### 5.5 Subject Withdrawal

Each enrolled study subject shall remain in the clinical investigation until completion of the required follow-up period; however, a subject's participation in any clinical investigation is voluntary and the subject has

## Clinical Investigation Plan

the right to withdraw at any time without penalty or loss of benefit. Conceivable reasons for discontinuation may include, but not be limited to, the following:

- Subject death
- Subject voluntary withdrawal
- Subject lost-to follow-up as described below
- Subject's follow-up is terminated according to [Section 3.5].

The Sponsor must be notified of the reason(s) for subject discontinuation. The site will provide this information to the Sponsor. Investigators must also report this to their respective EC as defined by their institution's procedure(s).

No additional follow-up will be required or data recorded from subjects once withdrawn from the clinical investigation, except for the status (deceased/alive if subject agrees).

However, if a subject withdraws from the investigation due to problems related to the safety or performance of the device under investigation, the investigator shall ask for the subject's permission to follow his/her status/condition outside of the clinical investigation.

### 5.5.1 Lost-to-Follow-up

If the subject misses two consecutive scheduled follow-up time points and the attempts at contacting the subject detailed below are unsuccessful, then the subject is considered lost-to-follow-up. Site personnel shall make all reasonable efforts to locate and communicate with the subject (and document these efforts in the source documents), including the following, at each contact time point:

- A minimum of two telephone calls on different days over the specified follow-up windows to contact the subject should be recorded in the source documentation, including date, time and initials of site personnel trying to make contact.
- If these attempts are unsuccessful, a certified or registered letter should be sent to the subject.
- If a subject misses one or more non-consecutive follow-up contact time points, it will be considered a missed visit. The subject may then return for subsequent visits. If the subject misses two consecutive time points and the above-mentioned attempts at communicating with the subject are unsuccessful, the subject will be considered lost-to-follow-up.

**Note:** Telephone contact with General Practitioner, non-clinical investigation cardiologist or relative without the presence of the subject or indirect documentation obtained via discharge letters will not be considered as subject contact.

### 5.6 Total Expected Duration of the Clinical Investigation

### 5.7 Expected Duration of Each Subject's Participation

The expected duration of each subject's participation in the clinical investigation is 12 months.

## Clinical Investigation Plan

### 5.8 Number of Subjects

Up to 200 subjects will be enrolled in the clinical investigation, with a predefined minimum of 73 subjects required to analyze the primary safety endpoint. No site may enroll more than 20% of the maximum number of enrolled subjects (n=40).

### 5.9 Estimated Time Needed to Select Required Number of Subjects

## 6 TREATMENT AND EVALUATION OF ENDPOINTS

For patients that have successfully completed screening and been approved by the SSC, scheduled visits will be performed in the following order: Baseline, Index Procedure, Discharge, 30-day, 6 months and 12 months. A description of study-specific assessments to be performed at the scheduled visits is provided in APPENDIX IV.

### 6.1 Baseline Assessments

#### 6.1.1 Baseline Laboratory and Clinical Tests

Patients who are deemed eligible for transfemoral implantation of a Portico™ valve using the FlexNav™ Delivery System will undergo a baseline visit within 14 days of the scheduled implant procedure (may occur on the day of, but prior to the implant procedure).

The following baseline data will be collected for all subjects prior to the index procedure.

1. Chest X-ray
2. Cardiovascular medications documentation (including dosage)
3. Modified Rankin Scale (mRS)
4. NIH Stroke Scale (NIHSS)
5. Barthel Index
6. Quality of Life Measures (SF-36, EQ-5D and KCCQ)
7. Mini Mental State Exam (MMSE-2:SV)
8. Six Minute Walk Test (6MWT)
9. Lab Measurements (Troponin or CK/CK-MB, INR if subject is on Coumadin or Warfarin or other anticoagulants/vitamin K antagonists in lieu of warfarin)
10. Adverse events assessment

Excluding the chest X-ray scan which is standard of care and will be conducted per hospital guidelines, all baseline assessments are considered study-related assessments.

## Clinical Investigation Plan

### 6.1.2 Pre-procedure Antiplatelet/Anticoagulation Medications

Antiplatelet/Anticoagulation and other medications should be administered pre-procedure per the standard of care at the investigational site.

### 6.1.3 Pre-Procedure Blood Test

The following blood tests will be performed at the investigational site within 72 hours prior to the index procedure:

1. Cardiac enzymes (Troponin or CK/CK-MB)
2. BUN and Creatinine

## 6.2 Index Procedure

### 6.2.1 Procedure Involved in the Use of the Investigational Devices

Please refer to IFU for instructions on handling and preparation of the FlexNav™ Delivery System, FlexNav™ Loading System and Portico™ valve. All Investigators must read and understand the IFU and Investigator Brochure.

### 6.2.2 Anticoagulation Therapy

Anticoagulation use during the procedure is left to the physician's discretion or should be established as with any other biological valve implantation, considering risks and benefits for the patient. The activated clotting time (ACT) should be monitored and recorded on source documentation during the procedure and medications should be adjusted to attempt to keep the subject's ACT>250 seconds.

### 6.2.3 Treatment Procedures

The local heart team's interventional cardiologist(s) and cardiac surgeon(s) must jointly participate in the intra-operative technical aspects of the TAVR procedure.

It is strongly encouraged that the index procedure occur within 14 calendar days following SSC approval.

At least one transcatheter aortic valve may be implanted in a subject who has signed the Informed Consent Form, and Data Protection Form (if applicable). Although not recommended, if a physician determines it is in the best interest of the subject to have a second transcatheter aortic valve placed, a subject may receive an additional transcatheter aortic valve (Valve-in-Valve).

Standardized imaging techniques will be used during the index procedure to implant the valve and to assess valve performance and coronary patency.

The following data will be collected during the implant procedure:

1. Device access, deployment and final valve placement data collection
2. Aortic systolic/diastolic pressure, mean aortic pressure, mean aortic valve gradient, peak aortic valve gradient and aortic regurgitation (post-implant only) immediately pre- and post implant,
3. If performed, right atrial pressure, pulmonary artery systolic/diastolic pressure, mean pulmonary artery pressure, pulmonary wedge pressure (PCWP) immediately pre- and post implant
4. Cardiac Rhythm Monitoring

Rhythm changes will be monitored and recorded at the following time points:

## Clinical Investigation Plan

- a) Upon crossing native valve with the guidewire
- b) Upon positioning of the guidewire
- c) Prior to valvuloplasty (if performed)
- d) Immediately post valvuloplasty (if performed)
- e) Before valve crosses the AV valve
- f) After valve crosses the annulus
- g) After valve is deployed in final position

5. Procedural information and imaging (angiogram, cine, intra-procedure echocardiography to be available to the Sponsor and provided upon request by the site)

Investigational sites should follow study-specific guidelines for the assessment of aortic regurgitation and implant depth. Refer to APPENDIX XVIII for a description of standardized methods for measuring aortic regurgitation according to VARC II criteria and instructions for assessing implant depth in the LVOT.

During the procedure, the implanting physician may determine implantation of the Portico™ valve is either not feasible or not in the best interest of the patient. Reasons may include, but are not limited to, anatomy that is not suitable for implantation, inability to gain access, ventricular arrhythmia, or any other contraindication.

If the implant procedure was not attempted (i.e. the FlexNav™ Delivery System was never introduced into the subject's vasculature), the subject will not be considered enrolled. Refer to Section 5.4 Subject Enrollment.

If the implant procedure was attempted (i.e. the FlexNav™ Delivery System was introduced into subject's vasculature) but the Portico™ valve could not be implanted (e.g. Portico attempted but other valve ultimately placed in the annulus), the subject will be withdrawn from the study after a 30-day adverse event collection period.

All the required information must be recorded on the applicable CRF.

Sponsor Representatives will be involved in providing support during the implant procedure.

Following the procedure, the FlexNav™ Delivery and Loading Systems should be securely disposed as per hospital requirements for hazardous materials. If there are any concerns noted with the FlexNav™ Delivery System, FlexNav™ Loading System, or Portico™ valve during the procedure, they should be returned to the Sponsor for evaluation per the instructions provided in

## Clinical Investigation Plan

APPENDIX XIX and APPENDIX XX.

### 6.2.4 Final (Post-procedure) Imaging

Subjects implanted with a transcatheter aortic valve (Portico™ valve or other commercially-available valve) will be required to undergo an echocardiogram within 48 hours of the procedure.

### 6.3 Post-procedure (In-hospital)

#### 6.3.1 Post-procedure Laboratory and Clinical Tests

The following laboratory tests should be performed in-hospital post-implant procedure:

1. Troponin, or CK / CK-MB should be collected within approximately 12-24 hours after procedure, approximately 24 hours thereafter, and at approximately 72 hours after the procedure (or at discharge, if patient is discharged prior to 72 hours post procedure).
2. BUN and Creatinine to be collected within 72 hours after index procedure

### 6.4 Discharge Plan

The discharge visit will take place at the time of hospital discharge or up to 7 days after the procedure, whichever occurs first. If the subject is expected to be discharged over the weekend, the discharge tests may be completed on the last work day prior to discharge.

The discharge assessment will include:

1. Physical exam (weight, heart rate, blood pressure)
2. Canadian Cardiovascular Society (CCS) Angina Scale Assessment
3. Modified Rankin Scale (mRS)
4. NIH Stroke Scale (NIHSS)
5. Barthel Index
6. Echocardiogram (if not performed during the post procedure testing within 48 hours after procedure)
7. 12 lead ECG (for subjects receiving a new permanent pacemaker, ECG should be completed showing the underlying rhythm as well as the current pacing programming)
8. Cardiovascular medications documentation
9. Adverse events assessment
10. Lab Measurements (CBC and Platelet count, BUN and Creatinine, and Troponin or CK/CK-MB if patient is discharged prior to 72 hours post-procedure)

## Clinical Investigation Plan

### 6.5 Follow Up Visits

#### 6.5.1 Follow-up Medications

Medications administered to subjects during the follow-up period will at the physician's discretion and should be prescribed according to current guidelines and standard of care.

#### 6.5.2 Follow-up for All Enrolled Subjects

Required clinical follow-up will be performed at the following intervals for all subjects who underwent a Portico implant attempt and were implanted with a Portico™ valve:

- 30 days (-7 days/ +21 days) follow-up site visit (visit must be conducted even if subject is in hospital)
- 6 months (180 days  $\pm$  30 days) follow up site visit
- 12 months (365 days -30 days, +45 days) follow up site visit

Subjects with a Portico implant attempt that did not have a Portico™ valve implanted will only be required to complete the 30 day follow up visit.

Follow-up visits will be calculated from the date of the implant procedure. Follow-up assessments can be performed at any point within the pre-specified follow-up visit window, and should be conducted, whenever possible, by the same individual who performed the baseline tests.

Every effort should be made by the study site to have the subject return to the investigational site for all follow-up visits. If, despite all efforts, the subject is unable to return to the study site during a follow-up window, subjects may undergo a remote follow-up assessment to collect applicable data. Remote assessments should include telephone contact with the subject and/or a visit to a medical facility with all data that can be reasonably and legally collected remotely on the study subject. Follow-up visits occurring at non-study sites will be limited to standard of care data collection only. Authorization for the release of medical records from non-study facility is the responsibility of the investigational site. Protocol deviations will be required for all missed testing.

An enrolled subject may only be followed at another investigational site with prior agreement from that site's Investigator and from the Sponsor.

Each site will be responsible for performing and interpreting the follow-up echocardiograms using the VARC-2 definitions. Echocardiograms will be sent to an independent Echocardiographic Core Laboratory for further analysis. Exams should be recorded in DICOM format and should be de-identified prior to sending to the Sponsor.

#### 6.5.2.1 30 Day Follow-Up

The 30-day follow-up visit will take place 30 days (-7/+21 days) post-index procedure, and will include the following assessments:

1. Physical exam (weight, heart rate, blood pressure)
2. Canadian Cardiovascular Society (CCS) Angina Scale Assessment
3. Modified Rankin Scale (mRS)

## Clinical Investigation Plan

4. NIH Stroke Scale (NIHSS)
5. Barthel Index
6. Echocardiography
7. 12 lead ECG (for subjects receiving a new permanent pacemaker, ECG should be completed showing the underlying rhythm as well as the current pacing programming)
8. Lab Measurements (including CBC and Platelet count, BUN and creatinine, BNP or ProBNP, INR if subject is on coumadin, warfarin or other anticoagulants/vitamin K antagonists in lieu of warfarin, Troponin or CK/CK-MB and Albumin)
9. NYHA Functional Classification
10. Frailty Index Assessment (Katz Index of Activities of Daily Living, Grip Strength, 5 meter walk test)
11. Quality of Life Measures (SF-36, EQ-5D and KCCQ)
12. MMSE-2:SV
13. Six Minute Walk Test (6MWT)
14. Cardiovascular medications documentation
15. Adverse events assessment

### 6.5.2.2 6 Month Follow-Up

The 6-month follow-up visit will take place at 6 months ( $\pm 30$  days) post-index procedure, and will include the following assessments:

1. Physical exam
2. Canadian Cardiovascular Society (CCS) Angina Scale Assessment
3. Modified Rankin Scale (mRS)
5. NIH Stroke Scale (NIHSS)
6. Barthel Index
7. Echocardiography
8. 12 lead ECG (for subjects receiving a new permanent pacemaker, ECG should be completed showing the underlying rhythm as well as the current pacing programming)
9. Lab Measurements (including CBC and Platelet count, BUN and creatinine, BNP or ProBNP, INR if subject is on coumadin, warfarin or other anticoagulants/vitamin K antagonists in lieu of warfarin, Troponin or CK/CK-MB and Albumin)
10. NYHA Functional Classification
11. Frailty Index Assessment (Katz Index of Activities of Daily Living, Grip Strength, 5 meter walk test)
12. Quality of Life Measures (SF-36, EQ-5D and KCCQ)
13. MMSE-2:SV

## Clinical Investigation Plan

14. Six Minute Walk Test (6MWT)
15. Cardiovascular medications documentation
16. Adverse events assessment

### 6.5.2.3 12-Month Follow-Up

The 12-month follow-up visit will take place at 12 months (-30 days, +45 days) post-index procedure, and will include the following assessments:

1. Physical exam (weight, heart rate, blood pressure)
2. Canadian Cardiovascular Society (CCS) Angina Scale Assessment
3. Modified Rankin Scale (mRS)
4. NIH Stroke Scale (NIHSS)
5. Barthel Index
6. Echocardiography
7. 12 lead ECG (for subjects receiving a new permanent pacemaker, ECG should be completed showing the underlying rhythm as well as the current pacing programming)
8. Lab Measurements (including CBC and Platelet count, BUN and creatinine, BNP or ProBNP, INR if subject is on coumadin, warfarin or other anticoagulants/vitamin K antagonists in lieu of warfarin, Troponin or CK/CK-MB and Albumin)
9. NYHA Functional Classification
10. Frailty Index Assessment (Katz Index of Activities of Daily Living, Grip Strength, 5 meter walk test)
11. Quality of Life Measures (SF-36, EQ-5D and KCCQ)
12. MMSE-2:SV
13. Six Minute Walk Test (6MWT)
14. Cardiovascular medications documentation
15. Adverse events assessment

### 6.5.3 Unscheduled Follow-up

#### 6.5.3.1 Unscheduled Follow-Up Visits for Evaluation of Suspected Neurological Event

If the subject experiences a neurological event (trans-ischemic attack (TIA), stroke, or encephalopathy), the event should be documented on an adverse event form and further evaluation should be performed at an unscheduled visit 90 days ( $\pm 14$  days) from the date of the neurological event. The unscheduled visit will include the following assessments:

- Neurological Assessment conducted by a neurologist or a neurology fellow
- Modified Rankin Score (mRS)
- NIH Stroke Scale

## Clinical Investigation Plan

Refer to APPENDIX XV for a copy of the Modified Rank Score and APPENDIX XVI for a copy of the NIH Stroke Scale.

### 6.5.4 Patient Reported Outcome (PRO) Measures

The following PRO measures will be collected according to the CIP requirements to assess whether the health of subjects has improved since enrollment in the clinical investigation:

- EuroQoL (EQ) 5D-3L Questionnaire
- SF-36
- KCCQ
- Mini-Mental State Examination (MMSE-2)
- Canadian Cardiovascular Society (CCS) Angina Scale Assessment
- New York Heart Association Functional Classification
- Barthel Index

Refer to APPENDIX VIII-XIV for copies of the exact format and version of PRO measures that will be administered as part of the clinical investigation

The Principal Investigator, research coordinator or study designee will administer the patient-reported outcome (PRO) measures. It is important the subject understands the meaning of all words and instructions in the measures. The subject should be instructed to ask any questions about the measures if further explanation is needed. Once the PRO measures are completed, the research coordinator or study designee will review for completeness to verify that all questions have been answered according to the directions provided.

#### 6.5.4.1 EQ-5D-3L questionnaire

The EuroQol 5D 3 level version (EQ-5D-3L) questionnaire is a standardized instrument used as a measure of health outcome and quality of life. The self-administered questionnaire consists of two pages: the EQ-5D descriptive system and the EQ visual analogue scale (EQ VAS). The questionnaire is cognitively simple and takes only a few minutes to complete. The EQ-5D-3L descriptive system comprises the following five dimensions: mobility, self-care, usual activities, pain/discomfort and anxiety/depression. Each dimension has three levels: no problems, some problems, extreme problems. The EQ VAS records the respondent's self-rated health on a 20cm vertical, visual analogue scale where the endpoints are labelled '100 =Best imaginable health state' and '0=Worst imaginable health state'. This information can be used as a quantitative measure of health outcome as judged by the individual respondents. An EQ-5D health state may be converted to a single summary index by applying a formula that attaches weights to each of the levels in each dimension. Refer to APPENDIX X for the sample questionnaire.

#### 6.5.4.2 SF-36

The Medical Outcomes Study Questionnaire Short Form 36 Health Survey version 2 (SF-36 v2) is a widely used, validated questionnaire that provides an indicator of overall health status. The self-administered questionnaire consists of 10 items across eight separate domains (Vitality, Physical functioning, Bodily pain, General health perceptions, Physical role functioning, Emotional role functioning, Social role functioning, Mental health). The questionnaire takes approximately five to 10 minutes to complete; elderly subjects may require 15 minutes.

## Clinical Investigation Plan

Two sets of scores are derived from the SF-36; eight individual domain scores, and two summary scores, one for the physical component (PCS) and one for the mental component (MCS) summary scores. For each set of scores, two alternative approaches may be used in calculating scores: a normal, additive approach that produces 0-to-100 scores for the eight scales (with a lower score indicating more disability and higher scores less disability), and a norm-based approach that adjusts these raw scores to have a mean of 50 and a standard deviation of 10. Refer to APPENDIX XI for the sample questionnaire.

### 6.5.4.3 Kansas City Cardiomyopathy Questionnaire (KCCQ)

The Kansas City Cardiomyopathy Questionnaire (KCCQ) is a 23-item, validated, self-administered instrument that quantifies physical function, symptoms (frequency, severity and recent change), social function, self-efficacy and knowledge, and quality of life in patients with congestive heart failure or weakened heart muscle due to prior heart attacks, heart valve problems, viral infections, or other causes.

The KCCQ evaluates eight (8) clinically relevant domains including: physical limitations, symptoms (frequency and severity), change over time, self-efficacy and knowledge, social function and quality of life. The questionnaire requires, on average, 4–6 minutes to complete. The KCCQ is scored by assigning each response an ordinal value, beginning with 1 for the response that implies the lowest level of functioning and summing items within each domain. Missing values within each domain are assigned the average of the answered items within that same domain. Scale scores are transformed to a 0 to 100 range by subtracting the lowest possible scale score, dividing by the range of the scale and multiplying by 100. To facilitate interpretability, two summary scores were developed; functional status score and a clinical summary score where higher scores reflect better health status. Refer to APPENDIX XII for the sample questionnaire.

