### 4.2 Descriptive Endpoint(s)

A selection of descriptive endpoints including valve performance parameters, clinical function assessments and adverse events defined according to VARC 2 criteria will be assessed at 30 days and at 12 months as defined below. All descriptive endpoints will be summarized separately using descriptive statistics.

Descriptive endpoints to be assessed at 30 days and included in the CE Mark submission:

- Non-hierarchical composite of all-cause mortality, disabling stroke, life threatening bleeding requiring blood transfusion, acute kidney injury requiring dialysis, or major vascular complications at 30 days from the index procedure.
- All-cause mortality at 30 days from the index procedure.
- Disabling stroke at 30 days from the index procedure.
- Non-disabling stroke at 30 days from the index procedure.
- Life threatening bleeding requiring blood transfusion at 30 days from the index procedure.
- Major bleeding at 30 days from the index procedure.
- Acute kidney injury at 30 days from the index procedure.
- Minor vascular complication rates at 30 days from the index procedure.
- Permanent pacemaker insertion at 30 days from the index procedure.
- Paravalvular Leak (PVL) at 30 days from the index procedure.
- NYHA functional classification at 30 days from the index procedure.
- KCCQ Quality of Life (QOL) score from baseline to 30 days from the index procedure.
- Technical device success defined as successful vascular access, delivery and deployment of the Portico Valve; retrieval with the delivery system and correct positioning of a single valve in the proper anatomical location.

Additional descriptive endpoints to be assessed at one year but not included in the CE Mark submission:

- Composite of all-cause mortality or disabling stroke at one year from the index procedure.
- All-cause mortality at one year from the index procedure.
- Disabling stroke at one year from the index procedure.

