## Clinical Investigation Plan

3. Over the past 2 weeks, how many times did you have **swelling** in your feet, ankles or legs when you woke up in the morning?

Every morning	3 or more times a week, but not every day	1-2 times a week	Less than once a week	Never over the past 2 weeks
				

4. Over the past 2 weeks, how much has **swelling** in your feet, ankles or legs bothered you?

It has been ...

Extremely bothersome	Quite a bit bothersome	Moderately bothersome	Slightly bothersome	Not at all bothersome	I've had no swelling
					

5. Over the past 2 weeks, on average, how many times has **fatigue** limited your ability to do what you want?

All of the time	Several times per day	At least once a day	3 or more times per week but not every day	1-2 times per week	Less than once a week	Never over the past 2 weeks
						

6. Over the past 2 weeks, how much has your **fatigue** bothered you?

It has been ...

Extremely bothersome	Quite a bit bothersome	Moderately bothersome	Slightly bothersome	Not at all bothersome	I've had no fatigue
					

7. Over the past 2 weeks, on average, how many times has **shortness of breath** limited your ability to do what you wanted?

All of the time	Several times per day	At least once a day	3 or more times per week but not every day	1-2 times per week	Less than once a week	Never over the past 2 weeks
						

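### As written, the KCCQ missing-item rule gives a symptom-free subject a symptom-frequency domain score of 106.7 or 93.3, not 100, when one frequency item is skipped

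*Protocol*

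**What the plan says.** Protocol section 6.5.4.3 sets out KCCQ scoring as a sequence.

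- Each response receives an ordinal value, "beginning with 1 for the response that implies the lowest level of functioning and summing items within each domain".
- For skipped items: "Missing values within each domain are assigned the average of the answered items within that same domain".
- The domain sum is then put on a common metric, described this way: "Scale scores are transformed to a 0 to 100 range by subtracting the lowest possible scale score, dividing by the range of the scale", followed by multiplication by 100.

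The transformation applies to the scale score, not to each item. No item rescaling and no cap is visible. The section lists the domains as "physical limitations, symptoms (frequency and severity), change over time, self-efficacy and knowledge, social function and quality of life", but has no table assigning questions to domains.

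Appendix XII prints the questionnaire. Question 3, on swelling "in your feet, ankles or legs when you woke up in the morning", has five options, one of them "3 or more times a week, but not every day". Questions 5 and 7, on fatigue and breathlessness, have seven options, one of them "3 or more times per week but not every day". Question 9, on sleeping upright, has five.

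Protocol section 4.2 lists "KCCQ Quality of Life (QOL) score from baseline to 30 days from the index procedure" among the descriptive endpoints for the CE Mark submission, with a one-year counterpart. SAP section 1.4.2 repeats both.

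**The concern.** Replacing a missing item by the mean of the others is harmless when all items in a domain share the same response range. It fails when they do not. A mean of raw values dominated by 7-option answers can exceed the maximum of a 5-option item, and a mean pulled down by 5-option answers understates a 7-option item. The sum is then rescaled with a range that assumes each item stays within its own limits, so the rule can break the 0-100 range promised in the same paragraph.

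At stake is the KCCQ change from baseline. If the reported score includes symptom frequency, a skip at one visit and not the other produces an apparent change whose sign depends on which question was skipped. The distortion grows with the level of the answered items, so it is largest on good forms.

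**Working it through.** **Inputs.** Scoring rule: Protocol section 6.5.4.3. Option counts: Appendix XII, questions 3, 5, 7 and 9 with 5, 7, 7 and 5 options. Treating these four as the symptom-frequency domain is an inference from their wording.

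**The plan's own figure.** Minimum sum = 4. Maximum sum = 5 + 7 + 7 + 5 = 24. Range = 20. Score = (sum - 4)/20 x 100. With complete forms the stated range reproduces: all worst gives 0, all best gives (24 - 4)/20 x 100 = 100.

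**Symptom-free subject, one item skipped, rule as written.**

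| Skipped | Imputed value | Item maximum | Sum | Score |
|---|---|---|---|---|
| none | - | - | 24 | 100 |
| 3 or 9 | (7+7+5)/3 = 6.33 | 5 | 25.33 | (25.33-4)/20 x 100 = 106.7 |
| 5 or 7 | (5+7+5)/3 = 5.67 | 7 | 22.67 | (22.67-4)/20 x 100 = 93.3 |

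**Not confined to one record.** Over all 5 x 7 x 7 x 5 = 1,225 response patterns, compare the rule with imputation on the missing item's own range, 1 + (levels-1) x mean of (response-1)/(levels-1).

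- Question 3 or 9 missing: error 0 to +6.7 points, unweighted mean +3.3.
- Question 5 or 7 missing: error 0 to -6.7 points, unweighted mean -3.3.
- Every item in its top two options: mean error +6.1 or -5.8.

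With one item missing, a score above 100 arises only when all three answered items are at their best. A lesser case: question 3 skipped, with answers 6, 7 and 5 to questions 5, 7 and 9. The imputed value is 18/3 = 6, the sum is 24 and the score is 100 despite residual fatigue. Own-range imputation gives 1 + 4 x (5/6 + 1 + 1)/3 = 4.78, a sum of 22.78 and a score of 93.9.

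**If frequency and severity form one 7-item domain.** Questions 4, 6 and 8 print six columns; the sixth records absence of the symptom.

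- Severity scored 1-6: maximum 42, minimum 7, range 35. Skip question 3: 37/6 = 6.17, sum 43.17, score 103.3. Skip question 5: 35/6 = 5.83, sum 40.83, score 96.7.
- Severity scored 1-5: maximum 39, minimum 7, range 32. Skip question 3: 34/6 = 5.67, sum 39.67, score 102.1. Skip question 5: 32/6 = 5.33, sum 37.33, score 94.8. Skipping a severity item also gives 102.1.

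**Domains with equal-length items.** Physical limitation (question 1, five functioning levels), self-efficacy (10-11) and quality of life (12-14) each return 100 whichever item is skipped. The options for question 15 (social function) are not shown, so that domain was not checked.

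**The case against.** The best case on the other side accepts the arithmetic and disputes its reach.

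- **The endpoint may be immune.** Its name can be read as the quality-of-life domain, questions 12-14, where the effect is zero. Section 6.1.1 also groups the whole KCCQ under quality-of-life measures, so the name does not settle it. This stands as a condition on the point.
- **The grouping of items is inferred.** This stands. The out-of-range result survives the combined-domain reading, with smaller deviations.
- **The governing rule may lie elsewhere.** Section 6.5.4.3 sits among general instrument descriptions, and Protocol section 8 sends missing-data handling to the SAP. Protocol 8.8 and SAP 2.9 show headings but no readable text. A different rule there cannot be excluded, but 6.5.4.3 would still have to agree with it.
- **Few forms will be affected.** Section 6.5.4 has staff review each questionnaire for completeness, and no missing rate is given. If, as an assumption, 2-10% of forms lacked one frequency item, the group mean of that domain would shift by at most 0.02 x 6.7 = 0.13 to 0.10 x 6.7 = 0.67 points. Upward and downward errors would partly cancel. The means of +/-3.3 weight all patterns equally and condition on an item being missing; they are not expected trial effects.

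A reader might infer that any skipped item moves the overall KCCQ score to 106.7 or 93.3. The documents do not support that: those are scores of one domain, and arise only from questions 3, 5, 7 or 9. A reader might also infer that the bias favours subjects who improved. It follows the level of the answers, not improvement, and partly cancels in the change score if the same item is skipped at both visits.

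**Conclusion.** The rule as written contradicts the 0-100 range stated beside it. For a symptom-free subject with one frequency item skipped, the symptom-frequency score is 6.7 points too high or too low. The deviation is +3.3 or -3.3 points in a combined symptom domain with severity scored 1-6, and +2.1 or -5.2 with severity scored 1-5.

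This rests on a literal reading of section 6.5.4.3 and on the inferred item grouping. It matters for results only if the reported KCCQ score includes symptom frequency, and only for forms with a skipped frequency item, or with any skipped symptom item in a combined domain of unequal item lengths. Someone might read it as a weakness in the main CE Mark safety evidence. It is not: KCCQ is descriptive, the CIP summary lists no powered secondary endpoints, and the primary endpoint and the minimum of 73 subjects are unaffected. It is a small scoring error that should be corrected because it is cheap to correct.

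**What to change.** In Protocol section 6.5.4.3, replace the raw-average sentence so that a missing item is imputed on its own range: 1 + (levels-1) x the mean of (response-1)/(levels-1) over the answered items in the domain. For the symptom-free subject this gives 5 for question 3 or 9 and 7 for question 5 or 7, so the score is 100 whichever is skipped. Count only functioning levels. The sixth column of question 1, for activities not done or limited by something else, should be treated as missing.

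Keep the stated sum and transformation, so that complete forms do not change. Averaging items already rescaled to 0-100 would also stay in range, but would alter complete forms: with questions 3 and 9 at 5 and questions 5 and 7 at 1, the stated sum gives (12-4)/20 x 100 = 40, and the average of rescaled items gives (100+0+0+100)/4 = 50.

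Alternatively, replace the sentence with the instrument's scoring algorithm as actually programmed, provided it keeps scores within 0-100.

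In the SAP, name which KCCQ score is the endpoint, and make any KCCQ missing-item rule there agree with the Protocol. The cost is one sentence and one line of scoring code, with no new data.
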